3. BACKGROUND

a. Past Experimental and/or Clinical Findings

Currently, the preferred treatment regimen for patients with chronic rhinosinusitis (CRS) with and without polyps after endoscopic sinus surgery involves a nonstandardized combination of oral steroids and antibiotics. The European Position Paper on Rhinosinusitis and Nasal Polyps offers guidelines for surgeons in the appropriate therapies to improve patient symptoms based on data available in the literature to date. The use of oral steroids in CRS is associated with level IV evidence and a category C recommendation, indicating a lack of randomized controlled data to

support its use (1). Therefore, this almost universal current practice is perpetuated by anecdotal data and expert opinion. Furthermore, systemic steroids are associated with known significant side effects and potential drug interactions. These may be severe and include but are not limited to high blood pressure, hyperglycemia and diabetes, adrenal suppression, weight gain, glaucoma, osteoporosis, fluid retention, gastrointestinal bleeding, ulcers, and mood changes (2). Thus, oral steroids potentially pose a significant risk, have unproven benefit, and are not appropriate for repeated or longterm use – an unfortunate obstacle in treating a chronic disease. Recently, steroids dissolved in a saline irrigant have been increasingly used and proven to be effective in the routine management of CRS. Furthermore, several studies have suggested the utility and safe side effect profile of these medications; however, the data supporting their use as a perioperative treatment is distinctly lacking. While the data to support the utility of topical steroids in the treatment of CRS is evident, relatively few groups have explored topical steroid irrigations specifically as a peri-operative intervention. Fandino et al conducted a meta-analysis of 13 randomized clinical trails and cohort studies examining the use of topical steroids delivered via drops, sprays, nebulizers, or irrigations for patients with CRS with nasal polyps who had previously undergone endoscopic sinus surgery. According to his analysis, intra-nasal corticosteroids had a significant beneficial effect on symptom scores and a reduction in polyp scores. Additionally, the use of INCS decreased the rate of polyp recurrence, and did not alter adrenocorticotrophic hormones post-intervention, suggesting the intra-nasal delivery method to carry less risk than the oral version (3). Snidvongs et al conducted a study with 111 patients and reported significant improvement in symptom scores and endoscopy scores over those who did not receive postoperative topical steroids (4). Jang et al retrospectively evaluated 60 patients postsurgically who were treated with topical steroid deliveries and showed a significant decrease in quality of life and endoscopy scores after patients stopped their treatments (5). In summary, the data supporting the use of steroids in patients with CRS immediately after endoscopic sinus surgery is sparse. We, therefore, seek to more definitively elucidate the role and utility of steroid treatment in the peri-operative period. Furthermore, per our review of the literature, there has been no direct comparison of the traditional oral regimen to topical therapy (nasal spray). Could these be proven equally effective, topically delivered steroids may be considered as a replacement for systemic steroids. This would represent a significant shift and improvement in the current post-operative management of CRS. Patients would avoid the innumerable side effects of oral steroids, which are detailed above. Furthermore, while oral steroid usage is often limited by unwanted side effects, a topical regimen may be sustained over a prolonged period as a maintenance therapy if symptoms necessitate.

b. Findings from Past Animal Experiments

None

4. DRUGS, BIOLOGICS, REAGENTS, OR CHEMICALS USED IN THE STUDY

a. Commercial Drugs, Biologics, Reagents, or Chemicals

Commercial Product 1	
Name:	Prednisone
Dosage:	10-40mg daily
Administration Route	Oral
New and different use? (Y/N)	N
Commercial Product 2	
Name:	Flonase
Dosage:	50ug/spray
Administration Route	Nasal
New and different use? (Y/N)	N
Commercial Product 3	
Name:	NA
Dosage:	NA
Administration Route	NA
New and different use? (Y/N)	NA

5. PARTICIPANT POPULATION

a. Planned Enrollment

Based on a current rate of 12-15 endoscopic sinus surgeries weekly, as well as allowing for a significant percentage of patients who do not desire to participate in the study, we anticipate between 80 and 100 patients to enroll. The study will be conducted only at Stanford Hospitals and Clinics. Participants will be those with CRS with and without polyps who have been recommended and consented for endoscopic sinus surgery. These participants will be used because they suffer from the specific disease for which we endeavor to research alternative therapies

b. Age, Gender, and Ethnic Background

We will recruit patients >18 that are able to provide consent. There will be no gender or ethnic exclusions.

c. Vulnerable Populations

NA

d. Rationale for Exclusion of Certain Populations

Children will not be included in this study as it is not typical for endoscopic sinus surgery to be performed in this population. It is rare for them to develop the extent of disease that would require surgical intervention, and surgery, in fact, is often avoided as the sinuses have not fully developed in the pediatric population. Furthermore, they are unable to provide their own informed consent to participate in this trial.

e. Stanford Populations

NA

f. Healthy Volunteers

NA

g. Recruitment Details

Recruitment will be invitation only from the patient population seen in our Rhinology clinics. Patients will first be evaluated by our providers. If, based on that evaluation, endoscopic sinus surgery is recommended to them and they meet inclusion criteria, they will then be informed of the study and its purpose and importance. After this has been discussed, patients will be invited to participate if they so choose. Our nurse practitioner performs all study introductions and obtains consent. If there are any questions, Rhinology providers are always available for consultation. We do not intend to advertise to nor recruit within the general public. There will be no recruitment materials.

h. Eligibility Criteria

i. Inclusion Criteria

Age > 18
Able to provide informed consent
Chronic rhinosinusitis with or without nasal polypsis based on published diagnostic criteria
Patients undergoing endoscopic sinus surgery

ii. Exclusion Criteria

Age
Aspirin exacerbated respiratory disease
Allergic fungal sinusitis
Cystic fibrosis
Immunosuppression
Chronic steroid use
Steroid use within 30 days prior to surgery

i. Screening Procedures

Screening will be performed during clinic visits. First, it must be determined if a patient is a surgical candidate, which is a decision based on establishing the diagnosis of chronic rhinosinusitis by published diagnostic criteria. Furthermore, patients with this diagnosis must have failed maximum medical therapy. At the pre-operative appointment, a complete routine history will be taken as is standard in our clinics. This will include information regarding past medical history, past surgical history, current medications, social history, family history, and allergies. This information is readily available to us as a part of the electronic medical record. Patients must also confirm accuracy by filling out a questionnaire prior to their first encounter. No qualifying laboratory values are necessary.

j. Participation in Multiple Protocols

We do not anticipate that participants will be enrolled in more than one study. However, we will be sure to inquire before enrolling patients if they are actively participating in another study. If so, and our interventions may interfere in any way, we will not continue with the enrollment

process. We do not anticipate difficulty in recruiting the required number of patients, and, therefore, will defer to studies in which patients are already enrolled.

k. Payments to Participants

NA

l. Costs to Participants

The participant will accrue identical costs to any patient being evaluated and treated for chronic rhinosinusitis, which will vary tremendously based on insurance policies. During the process, costs that may accumulate include: clinic appointments, prescribed medications, surgical intervention, specialty evaluation. No additional costs will be charged based on participation in this study.

m. Planned Duration of the Study

The study duration is anticipated to be 12 months. Time allotted for screening of the participant will depend heavily on the time that elapses between the initial patient encounter in clinic and the date for which surgery is scheduled. This may require 1-6 months, and occasionally longer. Active study participation will begin at the surgical date and end at the 4th post-operative visit. Organization and analysis of the data will require 2-4 weeks.

6. RISKS

a. Potential Risks

i. Investigational devices

NA

ii. Investigational drugs

NA

iii. Commercially available drugs, biologics, reagents or chemicals

Oral Prednisone: The side effects of short courses of systemic steroids (<3 weeks) include stomach upset, weight gain, insomnia, hyperglycemia, hypokalemia, adrenal suppression, and mood changes. These can occur in up to 16% of patients, with stomach upset being the most common. These effects are all reversible after stopping the steroid. Topical Fluticasone: The side effects of topical steroids include dry throat, sore throat, nasal irritation, headache, nose bleeds. These are the more common side effects, the incidence of which is unknown. Rare and serious side effects include difficulty breathing, flu symptoms, and vision changes. Again, these typically improve after stopping the steroids. On very rare occasion, vision symptoms may be permanent. None of these interventions differ from those already being instituted by our staff.

iv. Procedures

See the risks of the commercially available drugs - None of these interventions differ from those already being instituted by our staff.

v. Radioisotopes/radiation-producing machines

NA

vi. Physical well-being

NA

vii. Psychological well-being

NA

viii. Economic well-being

NA

ix. Social well-being

NA

x. Overall evaluation of risk

Low - innocuous procedures such as phlebotomy, urine or stool collection, no therapeutic agent, or safe therapeutic agent such as the use of an FDA approved drug or device.

b. International Research Risk Procedures

NA

c. Procedures to Minimize Risk

Medication administration will be monitored during the post-operative visits. Patients will begin their assigned therapy the day after surgery, and then will be seen 1, 2, and 4 weeks post-operatively. Any side effects being encountered will be discussed at these visits, and specialty services available in a timely manner to address them if needed. Furthermore, patients have 24 hour access to a physician in the department, and are, at any time, able to call with questions or concerns regarding their treatment.

Identifiable patient information will be handled per institutional protocol. Unique login information is required for all persons wishing to access the electronic medical system. All communications with patient data are sent on a secured machine via an encrypted service that is password protected.

d. Study Conclusion

The study will officially terminate for each patient after the 4th post-operative visit.

If a patient is experiencing an adverse outcome from surgery or from post-operative therapy, their participation in the study will be terminated early in the interest of well-being. In this event, patients will be promptly seen in subspecialty clinics (or by inpatient consultants if the patient is

admitted to the hospital) that may assist in managing these complications. Additionally, if a patient is having an emergency, they are able to contact one of our house staff 24 hrs per day for advice. As a last resort, our Emergency Department is available for expedited work up of major events.

Finally, if it becomes clear after the first 50 patients have completed their interventional therapy that one therapy arm is drastically superior to others, and that patients are thus not receiving optimal care, the study will be terminated and therapies altered.

e. Data Safety Monitoring Plan (DSMC)

- i. Data and/or events subject to review

Aggregate Data Analysis Reports Progress toward study endpoints AEs, SAEs, SUSARs

- ii. Person(s) responsible for Data and Safety Monitoring

The Protocol Director will be responsible for Data and Safety Monitoring.

- iii. Frequency of DSMB meetings

NA

- iv. Specific triggers or stopping rules

Currently, our post-operative protocol dictates that patients will be seen in clinic at 1 week, 3 weeks, and 6 weeks after surgery. We will only slightly alter this timeline for study patients. At the 2 week appointment, all experimental therapies will be completed. Patients will then be started on intranasal steroid sprays and saline irrigations so as not to deviate for an extended period from currently accepted practices. We will use the final scheduled appointment at 4 weeks after surgery as the official end point for comparison of treatment arms.

Additionally, outcomes evaluated will be the symptom questionnaire and the endoscopic exam score at each visit. If, during the course of follow up, one regimen proves to be clearly superior to another, the study will be terminated and patients will receive the optimal therapy. By power analysis, we require 50 patients to achieve statistical significance. If there is a clearly optimal therapy determined in these first 50 patients, we will end our research at that time. All patients will continue to be followed beyond 4 weeks depending on symptom severity and response to treatment.

- v. DSMB Reporting

NA

- vi. Will the Protocol Director be the only monitoring entity? (Y/N)

Y

- vii. Will a board, committee, or safety monitor be responsible for study monitoring? (Y/N)

f. Risks to Special PopulationsNA

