2. STUDY PROCEDURES

a. Procedures

Screening: Patients who have been recommended to undergo endoscopic sinus surgery by our department will be recruited for the study and informed of its purpose pre-operatively. SNOT22 scores (a quality of life survey well established in Rhinology) and Lund-Kennedy endoscopic exam scores (an quantitative clinical assessment of disease severity) will be recorded in their medical records. This is the same protocol performed for all patients seen in our clinic regardless of their enrollment in the study. Randomization and Treatment Groups: The patients that wish to participate will be randomized into two treatment arms by our nurse practitioner based on a random number generator. They will receive one of the following post-operative regimens: 1) oral steroid (treatment) + steroid spray (treatment) 2) oral placebo (control) + steroid spray (treatment) These medications will be manufactured and packaged by an independent compounding pharmacy, and prescribed by our nurse practitioner at the preoperative visit. Patients will begin their therapy on the first post-operative day. All oral steroid regimens will be given in our institution's standard 12 days taper, while topical steroids will be delivered via a metered dose nasal spray bottle for two weeks. All study patients will receive identical perioperative antibiotic therapy. We do not anticipate these medications to be an inconvenience to study patients as all proposed interventions are not different from routine post-operative care. In addition, patients undergoing surgery will have already trialed these medications as part of their pre-operative medical therapy. Surgery: Routine endoscopic sinus surgery will be performed per our institution's standard protocol. In this step there will be no difference in treatment from those patients not enrolled in the study. Post-Operative Care: At this point, patients will begin therapies according to the treatment arm to which they have been randomized. Study patients will attend post-operative appointments at identical time points to non-study patients. These will take place at the following intervals: Post-operative visit 1: 1-2 weeks Post-operative visit 2: 6-8 weeks Post-operative visit 3: 12-16 weeks Post-operative visit 4: 6 months Experimental therapy will finish after 2 weeks. At this visit, all patients will then be maintained on intranasal steroid spray and nasal saline irrigations, which is the commonly employed therapeutic standard. Thereafter, patients will, per standard protocol, be followed on an observational basis depending on the severity of symptoms and response to treatment. At each visit, as is done for all individuals, SNOT-22 and LundKennedy endoscopic exam scores will be repeated and recorded.

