
b. Procedure Risks

This study does not seek to evaluate a novel research procedure. Rather, we endeavor to determine if a procedure already in place nearly universally is, in fact, beneficial, as there is a

distinct lack of evidence of suggest so. Overall, we are investigating a procedural method that will have fewer side effects than the currently accepted practice.

c. Use of Deception in the Study

NA

d. Use of Audio and Video Recordings

NA

e. Alternative Procedures or Courses of Treatment

All reasonable alternatives are included as a treatment arm in this study. There is no standard of care that is being withheld from patients in any group.

f. Will it be possible to continue the more (most) appropriate therapy for the participant(s) after the conclusion of the study?

Yes, patients will stop all experimental therapies at the 2 week mark. They will then be placed on the typical post-operative regimen, which includes a nasal steroid spray and twice daily saline irrigations. They will continue to be followed in our clinic after the 4 week mark, and their therapies tailored to their current symptoms and the endoscopic appearance of the nasal cavity.

g. Study Endpoint(s)

Currently, our post-operative protocol dictates that patients will be seen in clinic at 1 week, 3 weeks, and 6 weeks after surgery. We will only slightly alter this timeline for study patients. At the 2 week appointment, all experimental therapies will be completed. Patients will then be started on intranasal steroid sprays and saline irrigations so as not to deviate for an extended period from currently accepted practices. We will use the final scheduled appointment at 4 weeks after surgery as the official end point for comparison of treatment arms. Additionally, outcomes evaluated will be the symptom questionnaire and the endoscopic exam score at each visit. If, during the course of follow up, one regimen proves to be clearly superior to another, the study will be terminated and patients will receive the optimal therapy. By power analysis, we require 50 patients to achieve statistical significance. If there is a clearly optimal therapy determined in these first 50 patients, we will end our research at that time. All patients will continue to be followed beyond 4 weeks depending on symptom severity and response to treatment

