Perioperative Oral Steroids for Chronic Rhinosinusitis Without Polyps

Statistical Analysis Plan

NCT02748070

July 2, 2020

[name], Principal Investigator
Stanford University
Stanford, California 94305

The planned sample size was 75 patients. By power analysis, we required 50 patients to achieve statistical significance. We collected outcome measures of SNOT-22 and Lund-Kennedy endoscopy scores at the following time points: preoperative baseline, and postoperatively at 1 week, 1 month, 3 months, and 6 months.

All statistical analyses were performed using Stata 15 (Stata Statistical Software: Release 15; StataCorp LP, College Station, Texas). SNOT-22 total scores, SNOT-22 subdomain scores, Lund-Kennedy endoscopic scores, and adverse effects were compared between prednisone and placebo groups at each time point using t-tests.

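### Adverse effects are compared between arms, but the one collection step described is discussion at visits and no on-treatment laboratory value is described, so the comparison can support a statement on reported effects only

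*Protocol*

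**What the plan says.** Safety is a large part of the reason for the trial. Protocol section 3 sets out the harms of systemic steroids, and section 7 aims to show that topical steroids work as well and are safer. Section 2b says in advance that "we are investigating a procedural method that will have fewer side effects than the currently accepted practice". The SAP makes adverse effects an analysed outcome: "Lund-Kennedy endoscopic scores, and adverse effects were compared between prednisone and placebo groups", at each time point, by t-test.

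On collection, section 6c (Procedures to Minimize Risk) says "Any side effects being encountered will be discussed at these visits". Section 6e lists adverse events, including serious ones, among the data for review. For routine assessments, section 2a says "At each visit, as is done for all individuals, SNOT-22 and LundKennedy endoscopic exam scores will be repeated and recorded". Neither document describes a form, checklist, definition, grading scale or onset date for side effects.

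Section 6a.iii names the short-course prednisone effects: "stomach upset, weight gain, insomnia, hyperglycemia, hypokalemia, adrenal suppression, and mood changes". It adds: "These can occur in up to 16% of patients, with stomach upset being the most common". The one statement about laboratory values is in the screening text of section 5: "No qualifying laboratory values are necessary". That concerns eligibility, not follow-up.

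**The concern.** An outcome that is compared between arms needs a stated and uniform way of being observed. Discussion may be prompted or unprompted, and may vary by clinician and visit; the documents do not say. Mild effects are the ones most easily lost, and most of the named effects can be mild. Biochemical changes without symptoms do not come up in conversation at all.

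What is at stake is the safety conclusion. If no difference is found, it could be because the effects were not recorded. If a difference is found, it could be taken to cover glucose, potassium and adrenal function, which were not measured. The SNOT-22 and endoscopy comparisons are not affected.

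**Working it through.** **1. Which named effects the described collection can reach.** The list in section 6a.iii has seven entries.

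| Effect | Can a patient report it? | Measurement described? |
|---|---|---|
| Stomach upset | Yes | Not needed |
| Insomnia | Yes | Not needed |
| Mood changes | Yes | Not needed |
| Weight gain | Partly | No scheduled weight |
| Hyperglycemia | Only if symptomatic | No |
| Hypokalemia | Only if symptomatic | No |
| Adrenal suppression | Only if symptomatic | No |

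The count is 3 + 1 + 3 = 7. The biochemical share is 3/7 = 43%.

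**2. What under-recording does to the comparison.** Suppose a share *s* of events is captured, equal in both arms. The expected observed difference is *s* × (p1 − p2). Take p1 = 16%, the protocol's ceiling; the text does not say whether that is per effect or for any effect. The documents give neither a placebo rate p2 nor a capture share, so both are assumptions, shown over a range.

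| Assumed p2 | s = 1 | s = 0.5 | s = 0.25 |
|---|---|---|---|
| 2% | 14 points | 7 points | 3.5 points |
| 5% | 11 points | 5.5 points | 2.75 points |
| 8% | 8 points | 4 points | 2 points |

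Equal under-capture shrinks the difference in proportion. For silent biochemical change, *s* is close to zero under the described method, and so is the observable difference.

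**3. Which visits fall within the taper.** Section 2a starts therapy on the first post-operative day and gives a 12-day taper, so it runs over days 1 to 12.

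| Source | Early contacts | Position relative to day 12 |
|---|---|---|
| Protocol 2a | 1-2 weeks, then 6-8 weeks | Days 7-14, so inside or up to 2 days after; next is at least 42 − 12 = 30 days after |
| Protocol 6c | 1, 2 and 4 weeks | Day 7 inside; day 14 is 2 days after; day 28 is 16 days after |
| SAP | 1 week, then 1 month | Day 7 inside; about day 30 is 18 days after |

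Under the SAP's time points, an effect arising on days 8 to 12 would first be asked about some 18 days or more after its onset. Under section 2a, a patient whose first visit falls on day 13 or 14 has no contact during the taper. The three schedules do not agree, and the opportunity to record on-treatment effects depends on which one was followed.

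**The case against.** The strongest reply is that section 6c is patient-care text rather than a data-collection section, that section 6e lists adverse events for review, and that the SAP analyses them, so recording was clearly intended. That stands. A reader might infer that side effects were merely talked about and never recorded, or that questioning was unprompted; the documents support neither. What is missing is the method of eliciting them, and a list of data for review does not supply one.

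A reader might also infer that the three biochemical effects could not be detected at all. That goes too far. Sections 6c and 6d provide 24-hour access to a physician, specialty services and emergency work-up, so clinically apparent cases could come to light. The gap is mild or silent change.

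Section 2b might be read as a finding about side effects. It is a justification given in advance, since one arm omits oral prednisone. Section 7 states an aim, and the SAP draws no safety conclusion. The point therefore concerns what the planned comparison can support, not a claim already made.

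The oral placebo reduces uneven reporting between arms. It does not restore events missed in both, and the documents do not say who is blinded.

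It is tempting to attach a power figure. Power is low: at 37 per arm, Fisher's exact test has about 10% to 36% power for 16% against assumed placebo rates of 8% down to 2%, even with full capture. But the placebo rates and the equal split of 75 patients are assumptions, and the result moves when one patient changes arm: for 16% against 5%, 20.8% with 38 on prednisone and 37 on placebo, but 28.9% with 37 and 38. Those figures mainly reflect sample size. A checklist would not cure them, and this point does not rest on them.

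**Conclusion.** The point holds in limited form. Neither document specifies how adverse effects are elicited or recorded beyond discussion at visits, although the SAP compares them by arm. Mild effects can be under-recorded, and mild or silent forms of three of the seven named prednisone effects would go unrecorded. The comparison can therefore speak to reported effects and cannot support a general statement that one regimen is safer.

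The count of three in seven comes directly from the protocol's list and from the absence of any described on-treatment laboratory value. How far a true difference would shrink depends on capture shares and placebo rates that the documents do not give. The efficacy comparison is untouched. This is an inexpensive improvement that should be made, not a fault that invalidates the trial.

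**What to change.** - **Protocol 6c:** record side effects at each existing post-operative visit on a fixed yes/no checklist of the patient-reportable effects already listed in section 6a.iii for prednisone and the spray. Use identical wording in both arms and ask for the onset date.
- **SAP:** state that the adverse-effect comparison covers reported effects only and supports no conclusion on glucose, potassium or adrenal function.
- **Protocol section 7:** limit the aim of a safer therapy to match.
- **Visit schedule:** reconcile Protocol sections 2a and 6c with the SAP, so that it is clear which visits fall within the taper.

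The SAP is written in the past tense. If collection is complete, the form comes too late, but the limits on wording in the SAP and section 7 still apply, and the report should describe how side effects were actually gathered.

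The cost is a one-page form at visits that already take place, more minor background reports in both arms because patients are asked directly, and a narrower safety claim. Whether to add laboratory tests is a clinical decision and is not proposed here.

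### The Protocol Director is the only monitor, and the superiority rule, open throughout follow-up, needs arm comparisons for which no coding or separation is described

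*Protocol*

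**What the plan says.** Protocol section 6e (Data Safety Monitoring Plan) sets out the arrangement item by item.

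- **Who monitors (items ii and vi).** "The Protocol Director will be responsible for Data and Safety Monitoring". Item vi, which asks whether that person is the only monitoring entity, is answered yes.
- **Committee (items iii and v).** "Frequency of DSMB meetings" is marked not applicable, and so is DSMB reporting.
- **What is reviewed (item i).** "Aggregate Data Analysis Reports Progress toward study endpoints AEs, SAEs, SUSARs". The text does not say whether these reports are pooled, coded or unmasked.
- **Stopping rule (item iv).** "If, during the course of follow up, one regimen proves to be clearly superior to another, the study will be terminated". The same item adds: "If there is a clearly optimal therapy determined in these first 50 patients, we will end our research at that time". It names the data as follows: "outcomes evaluated will be the symptom questionnaire and the endoscopic exam score at each visit". Section 2g carries the same text.
- **A further wording (section 6d).** The trial also ends "if it becomes clear after the first 50 patients have completed their interventional therapy that one therapy arm is drastically superior to others".

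The SAP lists t-tests of prednisone against placebo at each time point. It mentions no interim analysis, no coded report and no person responsible for one.

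**The concern.** A rule that turns on one regimen being superior cannot be applied to data pooled across arms. Someone has to compare the arms, and the only person to whom the monitoring plan gives any task is the Protocol Director. The item iv wording sets no limit on when or how often this happens.

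Two things are at stake. First, an uncounted series of efficacy looks, held and acted on by the trial's leader, raises the chance of stopping on a random difference. Second, knowledge of an emerging result could influence the conduct of the trial for patients not yet enrolled or completed. The second risk is weaker here because the oral treatment is placebo-controlled.

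A related gap is that item iv is headed as the place for triggers and stopping rules but holds only the efficacy text of section 2g. It says nothing about how the adverse events listed in item i feed into a decision about the trial.

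**Working it through.** **1. The plan's own figure.** The 50 patients said to be required by power analysis cannot be reproduced, because no alpha, power, effect size or SD is given. Solving backwards with 25 per arm (1:1 allocation assumed) and two-sided 0.05, the detectable standardized difference is d = (z for alpha + z for power) × √(2/25):

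- 80% power: (1.960 + 0.842) × 0.283 = 0.79
- 90% power: (1.960 + 1.282) × 0.283 = 0.92

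The documents do not allow a choice between these, and nothing below depends on it. The figure of 50 matters here only as the time of the named look.

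**2. Patients outside the first 50.** The planned total is 75 in the SAP and 80 to 100 in protocol section 5a.

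- (75 − 50)/75 = 25/75 = 33%
- (80 − 50)/80 = 30/80 = 38%
- (100 − 50)/100 = 50/100 = 50%

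This counts exposure, not bias. Two features could enlarge it. The open wording permits looks before 50. The section 6d wording places the look when the 50 have finished interventional therapy, at about 2 weeks, which is before the 4-week endpoint of section 2g.

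**3. False-positive risk.** The documents give no threshold, so assume that each look is an unadjusted two-sided 0.05 test of one outcome, with information proportional to patients.

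*One look at 50 plus the final analysis at N.* The two test statistics have correlation r = √(50/N), and type I error = 1 − P(|Z₁| < 1.96 and |Z₂| < 1.96).

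| N | r | Type I error |
|---|---|---|
| 75 | 0.816 | 7.7% |
| 80 | 0.791 | 7.9% |
| 100 | 0.707 | 8.3% |

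*A look every 10 patients from 20, with the last at N* (200,000 simulated trials per row).

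| N | Looks | Type I error |
|---|---|---|
| 75 | 7 | 14.5% |
| 80 | 7 | 15.0% |
| 100 | 9 | 16.7% |

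**4. What is stated and what is inferred.** Sole-monitor status and the open stopping rule are stated. That the rule needs an arm comparison follows from its meaning. That the Protocol Director makes the comparison is an inference: the rule names no decision-maker, but it sits in a plan with only one responsible party.

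**The case against.** The strongest reply is that this is a small single-centre study of marketed drugs, rated low risk in section 6a, for which a sole monitor is an ordinary choice, and that the harm is easily exaggerated. Much of this stands. A reader might draw several stronger conclusions that the documents do not support.

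- **That the Protocol Director is shown unmasked results and decides alone.** Item i speaks only of aggregate reports, and reports coded A and B would fit the text.
- **That this person also enrols, treats or scores.** Sections 2a and 5g give consent and randomization to the nurse practitioner. Neither document names the endoscopy scorer.
- **That endoscopy scores would be biased by arm.** The control arm takes an oral placebo supplied through an independent compounding pharmacy. Knowing an aggregate difference does not reveal a patient's arm, so a scorer would also need individual allocation. SNOT-22 is a patient survey.
- **That tailored therapy would distort the main comparison.** Section 2f places tailoring after week 4, which section 2g makes the official endpoint. It could affect only the SAP's 3- and 6-month comparisons.
- **That harm leads to no action at all.** Section 6d ends an individual's participation after an adverse outcome. Its trial-level rule could be read to include harm, though it does not say so.

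It is also fair to say that the inflation in type I error comes from repeated looks without a threshold, whoever makes them. A bar for clear or drastic superiority stricter than p < 0.05 would give lower figures. What survives is that the plan calls for an arm comparison, leaves its number and timing open, names only the trial's leader as monitor, and describes no coding or separation.

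**Conclusion.** The point holds in a limited form. As written, the Protocol Director may hold repeated by-arm efficacy comparisons and act on them while 33% (of 75) or 38% to 50% (of 80 to 100) of patients are still to be enrolled or completed. The main consequence is a greater chance of stopping on a random difference: about 8% with one look at 50 plus the final analysis, and about 14% to 17% with a look every 10 patients from 20. Those error rates rest on assumed unadjusted two-sided 0.05 tests and an assumed schedule of looks, so they illustrate the risk and do not estimate it for this trial. The documents do not show that unmasked results were seen, that scoring was biased, or that the Protocol Director scores or treats patients.

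**What to change.** - In sections 2g and 6e-iv, delete the sentence that allows termination for superiority at any time in follow-up.
- Keep only the look after 50 patients, and reconcile its wordings in 2g, 6d and 6e-iv. Have it prepared as coded groups by whoever runs the SAP analysis and, where possible, not by someone who scores endoscopy.
- At all other times, give the Protocol Director efficacy data pooled across arms.
- Do not restrict safety review. Adverse and serious adverse events stay under continuous review. The efficacy text duplicated in 6e-iv must be reconciled with the event review listed in 6e-i.
- If the trial is already complete, as the SAP's past tense suggests, report instead who saw by-arm data, when, and whether it was coded.

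Under the assumptions above, dropping the open-ended looks brings type I error from about 14% to 17% down to about 8%. The remaining excess over 5% depends on the threshold used at the single look, which is a separate matter.

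The cost is protocol wording and one coded report, with no committee. The documents identify no analyst independent of care, so if none is available someone must be found. The Protocol Director gives up unrestricted sight of by-arm efficacy results.
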